present a viable option to safely enhance therapeutic outcomes and expedited treatment gains for exposure-based therapies. D-cycloserine is a partial glutamatergic NMDA receptor agonist that is approved by the United States Food and Drug Administration to treat tuberculosis in high doses, but works as a cognitive enhancer for psychosocial interventions in much lower doses (e.g., 50 mg). DCS has been found to enhance extinction (Walker, Ressler, Lu, & Davis, 2002) and associative learning (Quermain, Mower, Rafferty, Herting, & Lanthorn, 1994) across numerous animal and human studies (Davis, 2011; Fitzgerald, Seemann, & Maren, 2014).

Exposure-based psychosocial interventions that utilize these mechanisms have demonstrated greater therapeutic outcomes and/or expedited therapeutic gains when augmented with DCS relative to placebo across a variety of psychiatric disorders (e.g., anxiety disorders, obsessive-compulsive disorder, post traumatic stress disorder, schizophrenia; Gottlieb et al., 2011; McGuire, Lewin, & Storch, 2014a). Moreover, across multiple RCTs of DCS-augmented treatment, few side effects have been reported with no serious adverse events identified (Ori et al. 2015). Although the results from these RCTs have been mixed across disorders (McGuire et al. 2014a), they bear considerable promise. Indeed, DCS-augmentation of HRT may yield greater overall reductions in tic severity and/or expedited therapeutic gains resulting from enhanced extinction and associative learning.

5. Study Aims

Primary Aim#1: To examine whether a single session of HRT+DCS will produce faster reductions in tic severity relative to HRT+placebo for tics targeted in treatment.

Hypothesis#1: We hypothesize that HRT+DCS will produce faster reductions in tic severity relative to HRT+placebo for tics targeted in treatment on the Hopkins Motor/Vocal Tic Scale (HM/VTS).

6. Administrative Organization

This study will only take place at the University of California Los Angeles (UCLA). There are no other participating study sites, laboratories, data management centers, and/or coordinating centers.

7. Study Design

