This is a double-blind placebo controlled study that will compare the efficacy of a single session of HRT augmented by either DCS or placebo in youth (age 8-17) who have either Tourette Disorder or a Persistent Tic Disorder. The sample size was determined based on the feasibility of the recruitment period. Participants will complete an initial evaluation to determine eligibility (Visit 1). Afterward, eligible youth will be randomly assigned to receive either DCS or placebo prior to a single session of HRT (Visit 2). During this visit, two tics will be targeted for treatment using HRT. One week after the therapy session, youth will return (Visit 3) to complete a follow-up assessment to determine improvement in tics targeted in treatment. The primary outcome measure will be the improvement in two bothersome on the Hopkins Motor/Vocal Tic scale (HM/VTS) at Visit 3.

8. Study Procedures:

Participants:

Included in this study will be up to 20 children and adolescents between the ages of 8 and 17

years (inclusive), who meet diagnostic criteria for Tourette Disorder or a Persistent Tic Disorder and the inclusion and exclusion criteria.

Recruitment:

Recruitment will occur through the UCLA OCD, Anxiety, and Tic Disorder's Program, as well as the greater Los Angeles Community.

Inclusion/Exclusion Criteria:

Inclusion criteria for this study are as follows: (1) ages 8 years to 17 years (inclusive); (2) meet diagnostic criteria for either Tourette Disorder or a Persistent Tic Disorder; (3) moderate tic severity or greater as evidenced by a Yale Global Tic Severity Scale (Leckman, Riddle, Hardin, & Ort, 1989) total score greater than 13 (>9 for children with motor or vocal tics only); (4) be fluent in English; (5) be medication free or on a stable dose of a non-antipsychotic medication for 6 weeks with no planned changes. Co-occurring psychiatric disorders are permissible for enrollment.

Exclusion criteria for this study are as follows: (1) pregnant or breast feeding; (2) an unstable medical condition (e.g., a seizure disorder, kidney or liver disease); (3) current diagnosis of substance abuse/dependence; (4) lifetime diagnosis of schizophrenia, autism spectrum disorder, bipolar disorder, or psychosis; (5) evidence of a seizure disorder, kidney or liver disease, pregnant and/or breast feeding; (6) four or more previous sessions of HRT; or (7) currently taking an antipsychotic medication.

Procedures:

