The study will consist of three visits over 3 weeks. Visit 1 is a baseline visit to determine eligibility, Visit 2 is a single session of HRT with either DCS or placebo, and Visit 3 is a follow-up assessment to measure change in tic symptoms.

Prior to coming in for Visit 1, interested children and families will complete a brief telephone screen to evaluate eligibility criteria conducted by either the principal investigator or research staff. If children and families appear to meet eligibility criteria, they will be scheduled for a baseline assessment to ascertain eligibility for participation.

At Visit 1 (Baseline), children and parents interested to participate will meet with the PI and other research staff to provide a general explanation of the study including eligibility requirements, study aims, and study procedures. The PI will give the consent forms to the families and explain what the forms mean. Written informed consent will be required from parents and written assent from children. After consent and assent are obtained, children and their parents will complete an assessment battery to determine eligibility, evaluate co-occurring psychiatric conditions, and measure tic symptom severity and related constructs that may take up to 3 hours to complete. An experienced clinician will conduct the following semi-structured clinical interviews with parents and children to identify psychiatric diagnoses, tic severity, premonitory urge presence, most bothersome tics, and global tic severity: the Anxiety Disorder Interview Schedule-Parent and Child Version (ADIS-C/P); the Yale Global Tic Severity Scale (YGTSS); the Individualized Premonitory Urge for Tics Scale (I-PUTS); Hopkins Motor and Vocal Tic Scale (HM/VTS) and the Clinical Global Impression of Severity (CGI-S). Children will also be asked to complete a standardized 10 minute video observational protocol to identify the frequency and severity of tics (Himle et al. 2006). Parents will be asked to complete a

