demographic questionnaire, a parent-report of the child's tic severity called the Parent Tic Questionnaire (PTQ), and a rating scale of ADHD severity called the Swanson Nolan and Pelham Scale-4th edition (SNAP-IV). After completing the video observation protocol, children will be asked to complete a child-report of tic severity called the Child Tic Questionnaire (CTQ), a self-report Premonitory Urge for Tics Scale (PUTS) to measure the child's global premonitory urge, and a self-reported rating scale of puberty development called the Peterson Puberty Development Scale (PDS). For female participants who have had first menses, a pregnancy screen will be conducted. Interested participants who meet full eligibility criteria will be invited back to complete Visit 2 (HRT session) approximately 1 week later.

At Visit 2, participants will arrive and will be randomly assigned to receive either a 50 mg placebo pill or a 50 mg d-cycloserine pill. Evaluating clinicians, participants, and the therapist will be blind to randomization assignment, with only the study coordinator and research pharmacy having access to randomization assignment. As d-cycloserine typically takes 1 hour to become active in participants' system, children and adult will be re-administered the following rating scales to evaluate the current severity of the participant's tics, most bothersome tics, and premonitory urge: the CTQ; PTQ, HM/VTS and I-PUTS. Children will then be asked to complete a computer task to evaluate habit learning called the Weather Prediction task. Afterwards, children will complete a session of HRT that will target two tics in treatment as identified by the HM/VTS. After the participant has completed the session of HRT, the participant will be asked to practice the skills learned in the session over the next week and to document practices using a homework monitoring form. The therapist will complete a session summary sheet to evaluate the patient's mastery of the skills within session. After the completion of the HRT session, a standard side effect form will also be administered to the participant to assess for any side effects. Participants will be asked to return 1 week later for a follow-up assessment. Visit 2 may take up to 4 hours to complete.

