Descriptive statistics will be used to characterize the entire sample and two conditions (DCS, placebo). Independent sample t-tests and chi-square tests will be used to examine for between-group differences (DCS versus placebo) for continuous and categorical variables respectively. Although no significant differences in conditions are expected due to random assignment, any significant between group differences will be controlled for during data analysis. Given that co-occurring ADHD and alpha-2 agonists have been found to influence tic severity outcomes to HRT, these will interested a covariates at baseline.

The primary outcome in this study will be the reduction in bothersome tic severity on the HM/VTS for the two tics targeted in treatment. The average score for these two bothersome tics will be interested into a repeated measures analysis of variance (ANOVA), with the covariates of ADHD diagnosis and alpha-2 agonist status at baseline. The diagnosis of ADHD will be identified from the structured clinical interview (ADIS), and alpha-2 agnostic will come from demographic information form. This data will be entered across three assessment visits, with a between group factor of treatment condition (DCS+HRT or PLBO+HRT).

References

Achenbach, T. M., & Rescorla, L. A. (2001). *Manual for the ASEBA School-Age Forms & Profiles*. Burlington, VT: University of Vermon, Research Center for Children, Youth & Families.

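### The three-visit ANOVA does not say which effect tests DCS, and the group-by-visit test it implies does not isolate the Visit 3 outcome; a 1-df ANCOVA of Visit 3 would

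*Combined protocol and SAP*

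**What the plan says.** **Hypothesis (section 5).** The claim to be tested is that "HRT+DCS will produce faster reductions in tic severity relative to HRT+placebo for tics targeted in treatment".

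**Primary outcome (section 7).** The timing is given as one visit: "The primary outcome measure will be the improvement in two bothersome on the Hopkins Motor/Vocal Tic scale (HM/VTS) at Visit 3".

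**When HM/VTS is rated (section 8).**

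- Visit 1: the baseline battery includes the "Hopkins Motor and Vocal Tic Scale (HM/VTS) and the Clinical Global Impression of Severity (CGI-S".
- Visit 2: assignment to pill or placebo is described first. Then: "As d-cycloserine typically takes 1 hour to become active in participants' system, children and adult will be re-administered the following rating scales". The list ends "most bothersome tics, and premonitory urge: the CTQ; PTQ, HM/VTS and I-PUTS". The computer task comes next, and then: "Afterwards, children will complete a session of HRT that will target two tics in treatment as identified by the HM/VTS".
- Visit 3, one week later: "Visit 3 is a follow-up assessment to measure change in tic symptoms". HM/VTS is part of that battery.

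**Analysis (section 11).** The outcome is the reduction in the two-tic mean, analysed by repeated measures ANOVA with ADHD diagnosis and alpha-2 agonist status as covariates: "This data will be entered across three assessment visits, with a between group factor of treatment condition (DCS+HRT or PLBO+HRT". The section names no interaction or contrast as the test. It also states no alpha, effect estimate or sphericity correction.

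**The concern.** Section 7 asks about one time point, Visit 3. The model in section 11 treats three ratings as outcomes, and two of them precede the HRT session that DCS is meant to augment. If the test is group-by-visit, one of its two degrees of freedom asks whether the arms changed differently between Visit 1 and Visit 2. HRT cannot have influenced that comparison.

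There are two consequences. A significant interaction does not by itself show benefit at Visit 3, because a difference in Visit 1-to-2 change can produce it. A 2-df test also yields no single adjusted difference with a confidence interval. In a trial of at most 20 participants whose size was set by feasibility, that interval is the most useful result. Some power is also spent on the pre-HRT comparison.

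**Working it through.** **Inputs.** From the documents: up to 20 participants, three HM/VTS ratings, two covariates, and only Visit 3 after HRT. The documents give no power figure to reproduce, and no alpha, allocation ratio, effect size, SD or correlation. Assumed: two-sided 0.05; 10 per arm; equal SDs (set to 1); no dropout; effect d = 1.0 SD at Visit 3 only; correlation r from 0.5 to 0.8, either equal between all visits or serial (r between adjacent visits, r² between Visits 1 and 3). Section 4 describes a fluctuating course, so serial correlation is plausible.

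**Step 1: what the 2 df contain.** Group-by-visit splits into (i) Visit 3 against the mean of Visits 1 and 2, and (ii) Visit 1 against Visit 2. With equal correlation, contrast (i) has variance 1 + (1+r)/2 − 2r = 1.5(1−r), hence noncentrality d²/[1.5(1−r)·2/n] = n·d²/[3(1−r)]. At n = 10, d = 1, r = 0.5 this is 10/1.5 = 6.67. The whole 2-df interaction has the same noncentrality. So when the effect is at Visit 3 only, component (ii) adds a degree of freedom and no signal.

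**Step 2: ANCOVA on the pre-HRT mean.** The residual variance of Visit 3 given that mean is (1−r)(1+2r)/(1+r) for equal correlation and 1 − r²(1+r)/2 for serial.

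- Equal r = 0.5: 0.5·2/1.5 = 0.667. Noncentrality is 1/(0.667·0.2) = 7.5 on 1 and 15 df, giving power 73%. The interaction (6.67 on 2 and 32 df) has 59%.
- Serial r = 0.8: 1 − 0.64·0.9 = 0.424. Given Visit 1 alone it is 1 − 0.64² = 0.590. The t noncentralities are 1/√(0.424·0.2) = 3.4 and 1/√(0.590·0.2) = 2.9. This is why ANCOVA on Visit 1 alone loses power when correlation is strong and serial.

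**Step 3: simulated power.** These figures include two binary covariates (prevalence 0.5 and 0.3) and the Greenhouse-Geisser (GG) correction. They run lower than step 2 mainly because chance covariate imbalance costs precision.

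| Correlation | GG interaction | ANCOVA, pre-HRT mean | ANCOVA, Visit 1 only |
|---|---|---|---|
| Equal 0.5 | 51.5% | 64.7% | 59.8% |
| Equal 0.6 | 61.6% | 72.8% | 65.9% |
| Equal 0.7 | 75.0% | 82.9% | 75.8% |
| Equal 0.8 | 90.7% | 93.9% | 88.5% |
| Serial 0.5 | 43.1% | 56.3% | 50.4% |
| Serial 0.6 | 50.0% | 61.8% | 54.1% |
| Serial 0.7 | 61.7% | 70.4% | 59.1% |
| Serial 0.8 | 78.5% | 83.8% | 70.0% |

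The pre-HRT-mean ANCOVA gains from 93.9 − 90.7 = 3.2 to 64.7 − 51.5 = 13.2 points. The Visit 1 ANCOVA ranges from 59.8 − 51.5 = +8.3 to 70.0 − 78.5 = −8.5. Under no effect, the corrected interaction rejects in 4.3-5.1% of trials and the 1-df tests in 4.5-5.4%, so both are valid. Uncorrected, the interaction reached 7.6% in one uneven setting (correlations 0.9 for Visits 1-2 and 0.4 for the others).

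**Step 4: what a significant result means.** Suppose the arms differ by 0.5 SD at Visit 2 only and not at Visit 3. The documents give no basis for this figure; it only prices the risk. The interaction is then significant in 13-33% of trials, the pre-HRT-mean ANCOVA in 6-12%, and the Visit 1 ANCOVA in 5%.

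**Step 5: price of using Visit 2 as a baseline.** If DCS shifts the Visit 2 rating by s in the same direction as the Visit 3 effect, the pre-HRT-mean estimate becomes 1 − (s/2)·b. The slope b is r/[(1+r)/2] for equal correlation and r for serial.

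- Largest shrinkage: equal r = 0.8, s = 0.5. b = 0.889, so the estimate is 1 − 0.25·0.889 = 0.78.
- Smallest: serial r = 0.5, s = 0.3. b = 0.5, so the estimate is 1 − 0.15·0.5 = 0.93.

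At equal r = 0.8 with s = 0.5, power of the pre-HRT-mean ANCOVA is about 77%, slightly below about 79% for the interaction. The Visit 1 ANCOVA is not shrunk; its power there is about 88%.

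**The case against.** **The plan is nearly explicit already.** It names a treatment factor, three visits and an outcome of reduction, so most readers would infer group-by-visit. This stands: the gap is one unwritten phrase, and the implied test is valid once corrected. A reader might go further and infer that the plan has no test of DCS, or that the treatment main effect is the test. A main effect would average a Visit 3-only effect over three visits, with simulated power of 11-14%. Treating either effect as eligible would raise type I error to about 9.5%. The documents do not support that reading, because both the hypothesis and section 11 speak of reduction. Those figures should carry no weight here.

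**The gain is modest and assumed.** This stands for power. The scores are also not normal: if ratings are whole numbers from 0 to 4, a two-tic mean takes nine values. Section 11 may add covariates for baseline imbalance, and 10 per arm is a best case. The interpretive point does not depend on correlations: a 2-df p-value does not isolate Visit 3 under any of them.

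**Visit 2 may not be a clean baseline.** This stands. Section 8 appears to place the rating in the wait after the pill but does not state the exact order. Hence the sensitivity analysis and the fallback below.

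**Speed of reduction needs three visits.** This does not stand. With one rating after HRT, faster can only mean a larger reduction by one week, which is what the Visit 3 comparison tests.

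**Conclusion.** The point holds as an improvement in focus and reporting. Section 11 leaves the primary test unnamed, and the test it implies does not isolate the outcome in section 7 or give one effect estimate. A 1-df ANCOVA on the pre-HRT mean does both. It gains about 3 to 13 points of power over the corrected interaction in all eight assumed settings when the effect is at Visit 3 only.

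The gain is not universal: with a 0.5 SD pill effect on the Visit 2 rating and equal correlation 0.8, it becomes a small loss. It would be wrong to conclude that the planned ANOVA is invalid, or that this change cures the small sample. Confidence is high that the test is unnamed and unfocused, and moderate on which baseline to use, since that turns on an order of events that section 8 leaves unclear. Severity is minor to moderate.

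**What to change.** In section 11, before unblinding:

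1. **Primary test.** ANCOVA of the Visit 3 two-tic mean HM/VTS on treatment, the mean of the Visit 1 and Visit 2 pre-HRT scores, ADHD diagnosis and alpha-2 agonist status. Report the adjusted difference with 95% CI at two-sided 0.05.
2. **Sensitivity.** The same ANCOVA with the Visit 1 score alone as baseline.
3. **Supportive.** The three-visit ANOVA, with group-by-visit named as its test and the Greenhouse-Geisser correction stated.
4. **Order at Visit 2.** State in section 8 whether the HM/VTS rating precedes or follows the pill. If the rating cannot be treated as a baseline, make the Visit 1 ANCOVA primary.
5. **Targeted tics.** Say which visit's HM/VTS selects the two tics, and how a targeted tic without a Visit 1 rating is scored. The planned ANOVA needs this rule as much as either ANCOVA does.

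Cost: wording only, with no new visit, rating or participant. The ANCOVA uses one residual df (20 − 5 = 15 instead of 20 − 4 = 16). The pre-HRT mean carries the shrinkage risk in step 5 (1.0 to about 0.78-0.93 for an assumed 0.3-0.5 SD shift). The Visit 1 baseline avoids it but can lose up to about 9 points of power against the interaction when correlation is strong.

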Finally, the potential side effects associated with the administration of DCS include drowsiness, headache, prolonged or momentary dizziness, seizures, confusion, hallucinations, weakness, coma, rash, vitamin B₁₂ deficiency and/or folate deficiency (both of which may cause weakness and anemia), liver enzymes increases (which could cause weakness or bleeding), and shaking. However, these side effects are most commonly related with doses greater than 500mg/day and when dosed chronically (versus acutely), which is at least ten times greater than what we propose to administer in this study. DCS has been approved by the Food and Drug Administration for the treatment of tuberculosis for over 20 years, and, as discussed by Rothbaum et al. 2008, single-pill administrations have been associated with no adverse effects. Furthermore, a recent meta-analysis of over 20 randomized controlled trials of DCS-augmentation that included multiple doses of DCS within each trial, identified no greater adverse event profile relative to placebo with as many as 8 trials reporting no adverse events at all. In the event of a moderate or severe adverse event related to the medication, the subject will be withdrawn from the study, the attending psychiatrist ([name] will be notified), and the research staff will monitor the participant closely until the adverse reaction remits.

Although not a risk directly associated with d-cycloserine, there is always the chance that a participant may report either the perceived risk of suicidality or suicidality itself. In these cases, standard protocol will be followed. If, during an assessment, research staff determines that a

youth endorses a serious mental health program such as suicidal behavior, referral information and telephone numbers to appropriate community services will be provided. The PI will conduct a risk assessment for suicidal ideation and/or behavior. Although unanticipated, if the detected problem is imminent and of crisis status, the PI will take appropriate immediate action including calling emergency services and/or calling UCLA campus police to escort the youth to the emergency department (on-site at UCLA). These situations will be reviewed immediately with the PI's research mentor ([name]), who is a licensed clinical psychologist.

11. Analysis Plan

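### The primary repeated-measures ANOVA conventionally drops any child with a missing HM/VTS score, and no all-randomised analysis set is defined, although children can leave the study after dosing

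*Combined protocol and SAP*

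**What the plan says.** Section 11 puts the mean HM/VTS score of the two targeted tics into a "repeated measures analysis of variance (ANOVA), with the covariates of ADHD diagnosis and alpha-2 agonist status at baseline", and adds: "This data will be entered across three assessment visits, with a between group factor of treatment condition". It does not say which model term is the primary test, which children are analysed, or what happens when a score is missing. No sensitivity analysis is given anywhere. Section 7 places the primary outcome at Visit 3.

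On size, Section 8 says "Included in this study will be up to 20 children and adolescents between the ages of 8 and 17" and Section 7 says "The sample size was determined based on the feasibility of the recruitment period". There is no allowance for dropout.

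On timing, Section 8 (Procedures) says "At Visit 2, participants will arrive and will be randomly assigned to receive either a 50 mg placebo pill". HM/VTS is scheduled at Visit 1, again at Visit 2 before the HRT session (among "the CTQ; PTQ, HM/VTS and I-PUTS"), and at Visit 3. Visit 3 is therefore the only rating after HRT.

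On leaving the study, Section 10 says "In the event of a moderate or severe adverse event related to the medication, the subject will be withdrawn from the study". Section 9 ends participation after a serious adverse event. Neither section says whether the Visit 3 HM/VTS is still obtained.

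**The concern.** The plan is silent on missing data, but the method it names is not neutral. A conventional repeated-measures ANOVA needs a complete row for each child, so a child with two of three scores contributes nothing. Followed in the usual way, the plan lets the software choose the analysis set.

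Two routes to an incomplete row can be seen in the documents:

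- **Visit 3.** Children may leave after dosing under Section 9 or Section 10. Because the trigger follows the study pill, losses could differ by arm and could be related to outcome.
- **Visit 1.** The two target tics are taken from the HM/VTS, which is re-rated at Visit 2. Nothing requires both targets to have been rated at Visit 1.

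With at most 20 children, one deletion removes 1/20 = 5% of the sample or more. The groups compared may then no longer be the groups that were randomised.

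**Working it through.** The documents give no power, alpha, effect size, SD or dropout rate, so there is no planned figure to reproduce. What follows is an illustration under stated assumptions.

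**Inputs.** From the documents: N up to 20, three visits, Visits 1 and 2 before HRT, Visit 3 after. Assumed: 1:1 allocation (10 per arm), two-sided 5% test, SD 1 at each visit, correlation 0.6 between visits, true effect 1 SD at Visit 3 only, covariates ignored. Because Section 11 names no test term, the group-by-visit F test is taken as the plan's test. All effects are in SDs of a single-visit score.

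**1. The contrast.** Visit 3 minus the mean of Visits 1 and 2 has variance 1 + (1 + 0.6)/2 − 2 × 0.6 = 0.6 per child. The SE of the arm difference is √[0.6 × (1/n₁ + 1/n₂)]. At 10 + 10 this is √0.12 = 0.346.

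**2. Power with complete data.**
- Group-by-visit F test: the centred effect profile is (−1/3, −1/3, 2/3), with sum of squares 2/3. Noncentrality = (2/3) / [(1 − 0.6) × (1/10 + 1/10)] = 8.33 on 2 and 36 df. Power is 70%.
- Single contrast: noncentrality = 1/0.346 = 2.89 on 18 df. Power is 78%.
- Since 2.89² = 8.33, the signal is the same. The F test spreads it over 2 df, one of which compares the two pre-HRT visits, where no effect is assumed.

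**3. Visit 1 missing.** For the likelihood model with known covariance Σ, the visit means in an arm with k incomplete children have covariance [(10 − k)Σ⁻¹ + kΣₒ⁻¹]⁻¹, where Σₒ covers the observed visits.

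| Missing per arm | Complete-case SE | Likelihood SE | Ratio |
|---|---|---|---|
| 1 | √(0.6 × 2/9) = 0.365 | 0.351 | 1.04 |
| 2 | √(0.6 × 2/8) = 0.387 | 0.356 | 1.09 |

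**4. Visit 3 missing, DCS arm only.**

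| DCS children lost | Complete-case SE | Likelihood SE | Ratio |
|---|---|---|---|
| 1 | √[0.6 × (1/9 + 1/10)] = 0.3559 | 0.3551 | 1.002 |
| 2 | √[0.6 × (1/8 + 1/10)] = 0.3674 | 0.3657 | 1.005 |

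The gain is under 1%. Contrast power falls from 78% to about 75% (1/0.3559 = 2.81 on 17 df) or 72% (1/0.3674 = 2.72 on 16 df), and the model does not recover it.

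**5. Bias when 2 of 10 DCS children lack Visit 3** (simulation).
- Losses at random: about 0 with either analysis.
- The two with the worst Visit 2 scores are lost: the complete-case change analysis is off by 0.07 SD against DCS. Visit 3 adjusted for earlier scores is off by about 0.
- The two with the worst unseen Visit 3 scores are lost: 0.13 SD toward DCS complete-case and 0.19 SD adjusted. With no true effect, type I error is 6.3% and 8.3%.
- Loss only correlated 0.5 with the Visit 3 score: about 0.06 SD toward DCS complete-case and 0.09 SD with the likelihood model.

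**6. Chance of any missing Visit 3 among 20 children**, 1 − (1 − q)²⁰: 33% at q = 2%, 64% at 5%, 88% at 10%. These rates are assumptions.

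**The case against.** Section 11 never restricts the analysis to children with all three scores. That is inferred from how the method conventionally works, so part of the point is an omission. This stands, but the inference is a safe one and nothing in the plan counteracts it.

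A reader might infer a large power loss: about 70% falling to 50% if 30% of children lacked a pre-treatment score. The documents do not support that. Randomisation is at Visit 2, so every randomised child has attended Visits 1 and 2, where HM/VTS is scheduled. Participants may nominate up to five motor and five vocal tics, so a target not rated a week earlier should be uncommon. A Visit 1 gap is possible, but no rate can be derived.

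A reader might also infer that withdrawals will bias the result toward DCS. That is not shown either. Section 10 cites single-pill use without adverse effects and a meta-analysis finding no worse an adverse-event profile than placebo. Follow-up after dosing is one week, and visits are compensated. Step 5 shows bias in either direction, depending on who leaves.

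Finally, a mixed model is no cure for the likelier gap, a missing Visit 3. It gains under 1% in SE and can slightly increase bias when losses follow unseen scores. This stands, and it is why the model alone is not enough.

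**Conclusion.** The point holds in a limited form. The named method conventionally discards incomplete children, no all-randomised set is defined, and two sections remove children after dosing without saying whether the outcome is still collected. Bias is possible, not demonstrated, and of uncertain direction.

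Under the assumptions above, the clearest gain comes from naming one contrast: about 78% against 70% power with complete data. Using incomplete children saves 4% or 9% in SE if 1 or 2 per arm lack Visit 1, and almost nothing if Visit 3 is missing. All figures rest on the assumed correlation, effect size and 1:1 allocation. The missing analysis set and the silence about collecting Visit 3 do not depend on them.

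**What to change.** In Section 11:

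- Define the primary analysis set as all randomised children in the arm assigned.
- Replace the ANOVA with a likelihood-based repeated-measures model of the mean target-tic HM/VTS score. Include visit, arm-by-visit (a separate mean for each arm at each visit), ADHD diagnosis and alpha-2 agonist status, with small-sample degrees of freedom such as Kenward-Roger.
- Make the arm difference at Visit 3 relative to pre-treatment (the mean of Visits 1 and 2) the single primary contrast, with a 95% CI.
- Report numbers randomised and analysed per arm, with reasons for each missing Visit 3 score.
- Add a sensitivity analysis that varies the assumed values of missing Visit 3 scores.

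In Sections 9 and 10, reconcile the two different triggers for leaving the study, and state whether the Visit 3 HM/VTS is still collected afterwards.

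The cost is protocol wording and routine software. There are real limits. The model relies on data missing at random and estimates a few covariance parameters from 20 children. It does not restore power lost to a missing Visit 3, and it does not remove bias from losses driven by unseen Visit 3 scores. It also replaces a 2-df test with a 1-df contrast, so it changes the primary test even when data are complete and should be fixed before unblinding.
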